# 12.5 Endpoint Analysis

To evaluate changes in VO2max in subjects switching to *IQOS*, continuing to smoke cigarettes and being smoking abstinent.

A linear mixed effects model will be used to estimate the difference in VO2max between each arm (SA arm, *IQOS*-1 arm) versus cigarette arm one week after randomization (V4) and after completion of the 12-week training program (V43). The dependent variable will be the VO2max with baseline VO2max, arm, sex, age and baseline cigarette consumption as covariates. Self-reported cigarette consumption and/or *IQOS* use will be added as a covariate as well. Appropriate contrasts will be constructed to report an estimate of the VO2max and its 95% confidence intervals within each arm and also between SA arm, *IQOS*-1 arm vs cigarette arm. The comparison between SA vs *IQOS*-1 arm will be calculated as well.

To estimate the difference in  $VO_2max$  between *IQOS*-2 and other arms, the same model will be used to model the change between arms only at V43.

Other covariates may be added as deemed appropriate. The same analysis will be repeated for weight-adjusted and fat-free weight adjusted VO2max. Estimates of variability from the statistical model will be reported and may be used to power future similar studies.

To evaluate changes in exercise capacity in subjects switching to *IQOS*, continuing to smoke cigarettes and being smoking abstinent

The linear mixed effects model as described above for  $VO_2max$  will be used to estimate the difference in exercise capacity between the *IQOS*-1 or SA arm versus cigarette arm one week after randomization (V4) and after completion of the 12-week training program (V43). The dependent variable will be the time to complete the test in seconds with baseline exercise capacity (in seconds) as a covariate.

Other covariates may be added as deemed appropriate. Estimates of variability from the statistical model will be reported and may be used to power future similar studies.

To assess the intensity of the exercise training in subjects switching to *IQOS*, continuing to smoke cigarettes and being smoking abstinent

An appropriate statistical model will be used to estimate the intensity of exercise training in the various (cigarette, *IQOS*-1 and SA) arms over time. The exercise intensity will be the endpoint with baseline exercise intensity, age, visit, sex and arm as covariates. Self reported

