### **Confidentiality Statement**

Philip Morris Products SA	Clinical Study Protocol	Confidential
P1-EXC-01-EU	Version 3.0 / 2 May 2019	Page 105 of 151

cigarette consumption and/or *IQOS* may also be used as a covariate. Further details will be provided in the SAP.

Estimates of variability from the statistical model will be reported and may be used to power future similar studies.

Descriptive statistics will be used to present various measures assessing the intensity of exercise training in each arm. This includes the cumulative work produced (calories and calories/kg body weight), average work rate during each training session (watt and watt/kg body weight), average work rate during each interval during each training session (watt and watt/kg body weight), time spent at 0-50%, 50-65%, 65-75%, 75-90%, >90% of maximal work rate during each training session (min:sec), average heart rate (HR) during each training session (bpm) and time spent at 0-50%, 50-60%, 60-70%, 70-80 % and >80 % of maximal HR during each training session (min:sec).

To evaluate changes in physiological parameters and perception of exertion and capacity in subjects switching to *IQOS*, continuing to smoke cigarettes and being smoking abstinent

An appropriate statistical model will be used to estimate the differences in physiological parameters and perception of exertion and capacity whilst adjusting for covariates such as age, sex, cigarette consumption and/or *IQOS* use or any other clinically relevant covariates of interest. The difference between arms (*IQOS*-1/SA vs cigarette) will be estimated and reported together with its 95% confidence intervals. All other pairwise comparisons between arms will be estimated and reported as well.

To monitor trends of daily physical activity levels during the study in subjects switching to *IQOS*, continuing to smoke cigarettes and being smoking abstinent

Descriptive statistics of the various measures of physical activity as measured by the mHealth wearable device will be reported. An appropriate statistical (linear or non-linear) model will be used to estimate the levels of activity taking into account clinically relevant covariates such as sex, cigarette consumption and age, and repeated measures over time. Estimates for each arm and all pairwise comparisons between arms will be reported using an appropriate statistical model as defined in the SAP.

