6 SAMPLE SIZE JUSTIFICATION

The sample size of 20 per arm (smoking abstinence with training, IQOS with training, continued cigarette smoking with training) was determined based on previously published results, which reported a standard deviation of 14 mL/kg/min in VO₂max in the change

Confidentiality Statement

Philip Morris Products SA.	Statistical Analysis Plan	Confidential
P1-EXC-01-EU	Final 2.0	Page 30 of 71
Related to PMI-RRP-WKI-112487		SAD DI EYC OI EU

between groups which continued smoking and those who were smoking abstinent after participating in a 12-week training program (Albrecht, et al. 1998). This sample size allows a probability of 90% that the half-width of the 95% confidence intervals between two arms have a precision of approximately 10.3 mL/kg/min.

For example, if the mean difference in change between the cigarette arm and smoking abstinence arm was 12 mL/kg/min after training, we expect that if the experiment were repeated many times then on average 90% of the time the 95% confidence intervals of the mean differences between two arms will be within 1.7 and 22.3. To allow for a dropout rate of approximately 20%, the sample size will be 25 per arm. The IQOS-2 arm without training will mainly serve as a secondary analysis to the IQOS-1 arm with training, and the drop-out rate in this arm is expected to be lower. Therefore, only 15 subjects will be randomized to this arm.

CHANGES FROM THE PROTOCOL SPECIFIED STATISTICAL 7 ANALYSES

An exploratory analysis of VO2max and exercise capacity will be carried out on subjects with additional biochemical verification of smoking status.

8 **ANALYSIS SETS**

The main population for non-safety analysis will be the As Exposed Exercise Compliant Set. Safety will be analyzed using the Safety Set.

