Data and information contained in this document are considered to constitute trade secrets and confidential commercial information, and the legal protections provided to such trade secrets and confidential information are hereby claimed under the provisions of applicable law. No part of this document may be publicly disclosed without the written consent of Philip Morris Products S.A

Philip Morris Products SA.	Statistical Analysis Plan	Confidential
P1-EXC-01-EU	Final 2.0	Page 42 of 71
Related to PMI-RRP-WKI-112487		

will be excluded from this analysis. However, if the workload for all visits (V3, V4 and V43) were wrong but the same then the subject will be included in the analysis.

The comparisons of interest will follow Table 4 and Table 5 with estimates for within and between arms presented together with their 95% confidence intervals. A scatter plot of change in time to complete the test versus maximum work rate by arm will be plotted as well.

Other covariates may be added as deemed appropriate. Estimates of variability (e.g. "Covariance Parameter Estimates") from the statistical model will be reported (at least in the original statistical output listings) and may be used to power future similar studies.

A separate sensitivity analysis with all subjects including those with incorrectly calculated work load will be analyzed as well using the same analysis.

9.6.1.1.3 To assess the intensity of the exercise training in subjects participating in a training program switching to IQOS, continuing to smoke cigarettes and being smoking abstinent

The SAS procedure PROC MIXED will be used with the restricted maximum likelihood method for estimation of the intensity of exercise training in the various (cigarette, IQOS-1 and SA) arms over time. The change from baseline (defined as V5) in exercise intensity will be the endpoint with age, visit, sex, arm, visit*arm, baseline cigarette consumption at V1 and daily cigarette consumption as covariates. Endpoints to be analyzed as exercise intensity are

- Cumulative work produced during each training session (calories and calories/kg body weight)
- Average work rate during each training session (watt and watt/kg body weight)

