Estimates of the endpoints at V14, V28, V42 (corresponding to the end of the 1st, 2nd and 3rd month of training) and their 95% confidence intervals will be presented as per the comparisons listed in Table 5 except for IQOS-2 and Dual-2 groups as they did not participate in any exercise training. Estimates of study arms and pairwise comparisons of study arms will be tabulated over all visits as well as separately for each visit.

An example of SAS code for the model to be used is provided below:

```
proc mixed data= _DATA_ method=reml order=data;
class SUBJECT VISIT ARM SEX CC_CONS_GRP;
model ENDPOINT = ARM SEX AGE CC_CONS_GRP DAILY_CC_USE VISIT VISIT*ARM
/ddfm = kr;
random SUBJECT / subject = SUBJECT;
repeated VISIT / type=ar(1) subject = SUBJECT;
lsmeans ARM / diff=control("CC") CL alpha=0.05 bylevel e;
lsmeans ARM / diff=control("IQOS-1") CL alpha=0.05 bylevel e;
lsmeans VISIT*ARM / diff=control("VISIT#X" "CC") CL alpha=0.05 bylevel e;
```

Confidentiality Statement

Philip Morris Products SA.	Statistical Analysis Plan	Confidential
P1-EXC-01-EU	Final 2.0	Page 43 of 71
Related to PMI-RRP-WKI-112487		SAP P1-EXC-01-EU

```
lsmeans VISIT*ARM / diff=control("VISIT#X" "IQOS-1") CL alpha=0.05 bylevel
e;
run;
```

Estimates of variability (e.g. "Covariance Parameter Estimates") from the statistical model will be reported (at least in the original statistical output listings) and may be used to power future similar studies.

The average work rate during each interval at each training session, average heart rate during each training session, time spent at various percentages of maximal work rate and time spent at various percentages of maximal heart rate will be summarized using only descriptive statistics. For the time spent at maximal work rate or heart rate the data will be summarized at V5, V14, V29 and V41 as subjects will be on training program 1 at these visits.

9.6.1.1.4 To evaluate changes in physiological parameters and perception of exertion and capacity in subjects switching to IQOS, continuing to smoke cigarettes and being smoking abstinent

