lsmeans ARM / diff=control("IQOS-1") CL alpha=0.05;
```

Confidentiality Statement

Philip Morris Products SA.	Statistical Analysis Plan	Confidential
P1-EXC-01-EU	Final 2.0	Page 46 of 71
Related to PMI-RRP-WKI-112487		SAP_P1-EXC-01-EU
lsmeans MONTH*ARM / diff lsmeans MONTH*ARM / diff	ol("IQOS-2") CL alpha=0.05; =control("MONTH#X" "CC") CL =control("MONTH#X" "IQOS-1") =control("MONTH#X" "IQOS-2")	CL alpha=0.05;

The percentage of time active and percentage of time very active will be summarized on a monthly basis descriptively.

For each subject, average step counts will be plotted at baseline (V2-V3), Months 1 to 3. These will be presented as boxplots with step count on the y-axis and time on the x-axis for each product use group.

In addition, moving averages using a 7-day time window for daily step counts for all subjects will be plotted as well. If data is missing on one or more days, the average step count will be divided by the number of valid days available over the 7 day period. These will be plotted for all subjects versus day and color coded by product use arm. A separate plot will be created by averaging the daily moving average for each subject within a product use arm and plotted against time as well.

9.6.1.1.6 To describe changes in biological health markers in subjects switching to IQOS (with and without training), continuing to smoke cigarettes (with training) and being smoking abstinent (with training)

The SAS procedure PROC MIXED will be used with the restricted maximum likelihood method for evaluation of the biological health markers at V14, V28 and V43. The dependent variable will be the change from baseline of the biological health markers with age, sex, arm, visit, visit*arm, baseline cigarette consumption at V1 and daily cigarette consumption as covariates. Subject will be fitted as a random effect.

The baseline values of the parameters (V3) will be considered as covariate and other clinically relevant covariates of interest may be added as deemed appropriate. Estimates of the endpoints and their 95% confidence intervals within each arm will be reported and also between arms as per Table 5.

An example of SAS code for the model to be used is provided below:

```
proc mixed data= _DATA_ method=reml order=data;
class SUBJECT VISIT ARM SEX CC_CONS_GRP;
model CHANGE = BASELINE ARM SEX AGE CC_CONS_GRP DAILY_CC_USE VISIT
VISIT*ARM /ddfm = kr;
random SUBJECT / subject = SUBJECT;

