lsmeans VISIT*ARM / diff=control("14" "CC") CL alpha=0.05 bylevel e;
lsmeans VISIT*ARM / diff=control("14" "IQOS-1") CL alpha=0.05 bylevel e;
lsmeans VISIT*ARM / diff=control("14" "IQOS-2") CL alpha=0.05 bylevel e;
```

Confidentiality Statement

Philip Morris Products SA.	Statistical Analysis Plan	Confidential
P1-EXC-01-EU	Final 2.0	Page 47 of 71
Related to PMI-RRP-WKI-112487		SAP P1-EXC-01-EU
	diff=control("28" "CC") CL alpha	-
lsmeans VISIT*ARM /	diff=control("28" "IQOS-1") CL a	lpha=0.05 bylevel e;
lsmeans VISIT*ARM /	diff=control("28" "IQOS-2") CL a	lpha=0.05 bylevel e;
lsmeans VISIT*ARM /	diff=control("43" "CC") CL alpha	=0.05 bylevel e;
lsmeans VISIT*ARM /	diff=control("43" "IQOS-1") CL al	lpha=0.05 bylevel e;
lsmeans VISIT*ARM /	diff=control("43" "IQOS-2") CL al	lpha=0.05 bylevel e;
run;		

9.6.1.1.7 To describe changes in weight, body fat and waist circumference in subjects switching to IQOS, continuing to smoke cigarettes and being smoking abstinent

The SAS procedure PROC MIXED as described above for biological health markers will be used to evaluate the change from baseline in body fat and waist circumference (V4 and V43) with age, sex, visit, product use, visit*product use and daily cigarette consumption as covariates. Subject will be fitted as a random effect. Also the baseline values of the parameters (V3) will be considered as covariate and other clinically relevant covariates of interest may be added as deemed appropriate. Estimates within and between groups similar to those shown in Table 4 and Table 5 will be provided.

For body weight, the model presented in section 9.6.1.1.3 will be used to assess the changes at V14, V28 and V43 with change from baseline (V3) as the endpoint and age, sex, visit, product use, visit*product use and daily cigarette consumption as covariates. Subject will be fitted as a random effect. Also the baseline values of the parameters (V3) will be considered as covariate and other clinically relevant covariates of interest may be added as deemed appropriate. Estimates within and between groups at V14, V28 and V43 will be calculated together with their respective 95% confidence intervals.

Box plots for the change from baseline in weight for the study arms by month will be presented. For body fat and waist circumference we will present the study arms side by side separately for each visit (V4 and V43).

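### SAP 9.6.1.1.3 drops, without declaring it, the baseline-intensity covariate that Protocol 12.5 specifies for training intensity, at some cost in precision

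*SAP*

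**What the plan says.** Protocol 12.5, on the intensity of exercise training: "The exercise intensity will be the endpoint with baseline exercise intensity, age, visit, sex and arm as covariates". It then leaves the rest open: "Further details will be provided in the SAP".

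SAP 9.6.1.1.3: "The change from baseline (defined as V5) in exercise intensity will be the endpoint with age, visit, sex, arm, visit*arm". The only other covariates listed are cigarette consumption at V1 and daily cigarette consumption. The endpoints are cumulative work and average work rate per session, absolute and per kg. The example code agrees with the text: "model ENDPOINT = ARM SEX AGE CC_CONS_GRP DAILY_CC_USE VISIT VISIT*ARM". It has no baseline term. This section also lacks the sentence, present for VO2max and exercise capacity, that allows further covariates.

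SAP section 7, on changes from the protocol, lists one item only: "An exploratory analysis of VO2max and exercise capacity will be carried out on subjects with additional biochemical verification of smoking status".

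Elsewhere the SAP treats change scores differently. VO2max and exercise capacity carry the baseline value as a fixed covariate. The health-marker code has it ("model CHANGE = BASELINE ARM SEX AGE CC_CONS_GRP DAILY_CC_USE VISIT"). Body weight reuses the model of 9.6.1.1.3 and then adds: "Also the baseline values of the parameters (V3) will be considered as covariate".

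**The concern.** A covariate that the protocol names has disappeared between the two documents with no reason given. The SAP's other change-score models either include the baseline value or say that it will be considered, so this looks like an oversight.

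Objective 3 serves one of the study's stated goals, the ability to perform exercise training, and it was planned with 20 evaluable subjects per training arm. At stake are the width of its confidence intervals, its sensitivity to differences already present at V5, and the variance estimates, which the SAP says may be used to power later studies.

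**Working it through.** **The plan's own figure.** None is given for training intensity. The only precision figure concerns VO2max change (SD 14, 20 per arm). It reproduces: t(0.975, 38) × 14 × √(2/20) = 8.96, and 8.96 × √(χ²(0.90, 38)/38) = 10.23, against about 10.3 stated. That SD is for another endpoint and cannot be carried over.

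**What the omission does.** Let B be the V5 value and Y a later value. Modelling Y − B on arm is the same as modelling Y on arm with the coefficient of B fixed at 1. Once B is a covariate, Y and Y − B give identical arm contrasts. The change endpoint is therefore not the problem; the missing covariate is.

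**Variance at one later visit.** Set SD(B) = 1, SD(Y) = k, within-arm correlation ρ.

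- SAP form: 1 + k² − 2ρk
- With the covariate: k²(1 − ρ²)
- Difference: (1 − ρk)², never negative, and zero only when ρk = 1
- At k = 1, the ratio of adjusted to unadjusted is (1 + ρ)/2

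The documents give neither ρ nor k, so both are assumed. Extra CI width of the SAP form, √(unadjusted/adjusted) − 1:

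| k | ρ = 0.5 | ρ = 0.7 | ρ = 0.8 | ρ = 0.9 |
|---|---|---|---|---|
| 1.0 | 15.5% | 8.5% | 5.4% | 2.6% |
| 1.1 | 10.6% | 4.2% | – | 0.0% |
| 1.2 | 7.2% | 1.7% | – | 1.2% |
| 1.3 | 4.7% | 0.5% | – | 4.4% |

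**Small-sample cost.** With two arms of 20 and k = 1, half-widths in SD units that allow for the lost degree of freedom are 0.640 against 0.563 (ρ = 0.5), 0.496 against 0.464 (0.7), 0.405 against 0.390 (0.8) and 0.286 against 0.283 (0.9). The SAP form is then about 14%, 7%, 4% and 1% wider. At ρ = 0.95 the two are level (0.202 against 0.203). Simulation (4,000 replicates) gives standard errors of 0.309 against 0.272, 0.245 against 0.229, and 0.142 against 0.140 at ρ = 0.5, 0.7 and 0.9.

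**Carry-over.** Each 1 SD difference between arms at V5 moves the unadjusted contrast by ρk − 1, which at k = 1 is −0.5, −0.3 and −0.1 SD at ρ = 0.5, 0.7 and 0.9. With 20 per arm, a purely chance V5 difference has standard error √(2/20) = 0.32 SD and a 95% range of ±0.62 SD.

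**If the V5 difference is real.** Suppose a 0.5 SD product effect is already present at V5 and persists unchanged. In simulation the unadjusted contrast averages about 0. The adjusted contrast averages 0.24, 0.15 and 0.05 SD at ρ = 0.5, 0.7 and 0.9. Standard errors, unadjusted then adjusted, are 0.318 and 0.288, 0.243 and 0.233, and 0.143 and 0.147. A real V5 difference can thus cancel the precision gain when ρ is high.

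**Why ρ and k may vary by visit.** Protocol Appendix 2 puts V5 and V14 on training program 1, V28 on program 3 and V42 on program 2. SAP 8.3 counts a 40-minute session as complete from 20 minutes, so cumulative work at V5 may come from a shortened session.

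**The case against.** The strongest reply is that the SAP does not ignore baseline but removes it by subtraction, and that the protocol asks only for an appropriate model with details to follow. The protocol synopsis names no covariates for this model, and Protocol 12.1 says that changes in method will be documented in the study report. All of this is correct, and it softens the complaint about non-declaration. It does not explain why a named covariate went missing, or why section 7 is silent.

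The second reply is about the estimand. V5 is 15±2 days after randomisation, and SAP 9.6.1 groups subjects by actual product use. A V5 difference may be an early product effect or self-selection as well as chance, so adjusting for it is not a pure precision gain. This stands, but it does not favour the SAP model: the change score uses the same V5 value with slope 1 and removes all of a persistent early effect.

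Third, consistency within the SAP should not be overstated. For blood composition, respiratory parameters, health markers, body fat, waist and weight, the text says that baseline will be considered. The step-count example code also omits a baseline that its text lists, so absence from example code is weak evidence alone. Here text and code both omit it.

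A reader might go further and infer a gain in power, or a fixed saving of (1 + ρ)/2 in variance. The documents support neither. Protocol 12.1.5 and SAP 3.3.1 rule out hypothesis tests, and the formula needs equal SDs, which are not given.

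**Conclusion.** The discrepancy is real, undeclared and minor. The SAP form never has smaller residual variance than the protocol's and usually has more, apart from one degree of freedom. Its size cannot be fixed from the documents. Over ρ from 0.5 to 0.9, the extra CI width is about 15% down to 3% if V5 and later SDs are equal, 0 to 11% if the later SD is 1.1 to 1.3 times that at V5, and nil where ρk = 1. These figures assume a single later visit; those that include sample size also assume 20 per arm, and as-used group sizes may differ.

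The effect is on estimates, intervals and reported variances for an exploratory objective, with no bearing on a test or on the sample size. It would be too strong to say that only chance imbalance enters the contrast, or that restoring the term leaves the estimand unchanged.

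**What to change.** In SAP 9.6.1.1.3, add the V5 value of the intensity measure being modelled to the covariate list and the code (`model ENDPOINT = BASELINE ARM SEX AGE ...`), as Protocol 12.5 states. Say there that V5 is a post-randomisation baseline, so the contrast compares later sessions given V5 intensity and may not capture a product effect already present at V5. If the omission was intended, list and justify it in section 7.

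Optionally, add the highest wattage at the V3 VO2max test as a pre-randomisation covariate. It is already needed for the exercise capacity workload (Protocol 7.6.2). Neither document includes it in this model, so it is a suggestion and not a correction.

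The cost is one model degree of freedom, or two with the optional term. No new data are needed.

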9.6.1 Endpoint Analyses

The following non-safety endpoints will be analyzed using the AEECS considering the actual study arm (i.e. product use exposure). The following sections describe the statistical models used in analyzing the endpoints as well as descriptive statistics used for summarizing the data.

In general, for model based analysis all visit data will be used and analyzed within the same model.

- 9.6.1.1 Statistical Analysis of Endpoints
- 9.6.1.1.1 To evaluate changes in VO₂max in subjects switching to IQOS (with and without training), continuing to smoke cigarettes (with training) and being smoking abstinent

A linear mixed effects model will be used to estimate the difference in VO₂max between each arm (SA arm, IQOS-1+IQOS-2 combined arm, Dual-1+Dual-2 arm) versus cigarette arm one week after randomization (V4) and after completion (SA arm, IQOS-1 arm, IQOS-2 arm, Dual-1 arm) of the 12-week training program (V43). The degrees of freedom will be adjusted by using Kenward Roger (KR) method and the Saitterthwaite method will be used in case of convergence issues. Both V4 and V43 data will be used together in the same model. At V4, both IQOS-1 and IQOS-2 will be combined into a single IQOS group as these subjects did not attend any exercise training.

The dependent variable will be the VO₂max change from baseline with baseline VO₂max, arm, visit, sex, age and visit*arm as *fixed* covariates and subject fitted as a random effect. In addition, the following *exploratory* covariates BMI, RPC, COHb levels at each visit, cigarette consumption at V1, IPAQ score at V1, average step count 2 weeks prior to visit, self-reported daily cigarette consumption (from randomization until each visit), cigarette smoking 30-60 minutes before test for subjects in cigarette arm and IQOS use 30-60 minutes before test for subjects in IQOS arm will be assessed for adequacy in the model using a step-wise (backward) approach through the following algorithm.

Data and information contained in this document are considered to constitute trade secrets and confidential commercial information, and the legal protections provided to such trade secrets and confidential information are hereby claimed under the provisions of applicable law. No part of this document may be publicly disclosed without the written consent of Philip Morris Products S.A

Philip Morris Products SA.	Statistical Analysis Plan	Confidential
P1-EXC-01-EU	Final 2.0	Page 40 of 71
Related to PMI-RRP-WKI-112487		

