9.6.1.2.3 Intensity of exercise training

For the intensity of the exercise training recorded values will be listed. The following variables will be summarized at V5 (baseline), V14, V29 and V41 so that all subjects are on training program 1.

Confidentiality Statement

Philip Morris Products SA.	Statistical Analysis Plan	Confidential
P1-EXC-01-EU	Final 2.0	Page 49 of 71
Related to PMI-RRP-WKI-112487		

- Cumulative work produced during each training session (calories and calories/kg body weight)
- Average work rate during each training session (watt and watt/kg body weight)
- Average heart rate (HR) during each training session (bpm)

For cumulative work and average work rate they will be plotted for V5, V14, V29 and V41 using box plots with the response on the y-axis and month on the x-axis, within each month there will be a box plot for each product use category. Average heart rate will only be summarized and not plotted as the exercises are controlled for heart rate.

- Time spent at 0-50%, 50-65%, 65-75%, 75-90%, >90% of maximal work rate during each training session (sec)
- Time spent at 0-50%, 50-65%, 65-75%, 75-90%, >90% of maximal HR during each training session (sec).

For the time spent at maximum work rate or heart rate the data will again be summarized at only visits V5, V14, V29 and V41. Time spent at the various intervals of maximal work rate will be plotted using stacked bars for each product use group at each visit. Time spent in an interval of maximal heart rate will not be plotted.

Within each study arm the following variables will be summarized by interval (0-5, 6-20, 21-30, and 31-40 minutes) at V5, V14, V29 and V41.

- Intensity (%) {percent of maximal workload}
- Work rate (watt)
- Work rate per body weight (watt/kg body weight).

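### The training-intensity model measures change from V5 (Training 1) but reports it at V28 (Training 3) and V42 (Training 2), so the within-arm changes there mix programme content with change over time

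*SAP*

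**What the plan says.** On the model, SAP 9.6.1.1.3 states: "The change from baseline (defined as V5) in exercise intensity will be the endpoint". The endpoints are cumulative work and average work rate, each also per kg body weight. The covariates are age, visit, sex, arm, visit-by-arm, cigarette consumption at V1 and daily cigarette consumption. Visit is a class variable in the sample code.

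On reporting, the section gives "Estimates of the endpoints at V14, V28, V42 (corresponding to the end of the 1st, 2nd and 3rd month of training" and adds: "Estimates of study arms and pairwise comparisons of study arms will be tabulated over all visits as well as separately for each visit". The opening of SAP 9.6.1 says: "In general, for model based analysis all visit data will be used and analyzed within the same model". Table 15.2.2.3.1 in SAP 13.2 is titled for the change in cumulative work at V14, V28 and V42.

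For time spent at levels of maximal work rate or heart rate, the same section 9.6.1.1.3 says that "the data will be summarized at V5, V14, V29 and V41 as subjects will be on training program 1 at these visits". SAP 9.6.1.2.3 applies that rule to cumulative work and average work rate themselves, which "will be summarized at V5 (baseline), V14, V29 and V41 so that all subjects are on training program 1". Their box plots "will be plotted for V5, V14, V29 and V41 using box plots with the response on the y-axis and month on the x-axis".

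Protocol Appendix 2 tabulates which of the three programmes is used at each visit from V5 to V42. It leaves their intervals and intensities to a dedicated manual.

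**The concern.** A change score carries the meaning of its baseline. Here the baseline session is Training 1, while two of the three reported sessions are other programmes, which Appendix 2 describes as giving differentiated inputs. A rise or fall in work between V5 and V28 or V42 could come from adaptation to training, from the programme ridden that day, or from both. The planned estimate cannot separate them.

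The report would also carry two accounts of months 2 and 3 for one endpoint: modelled changes from Training 3 and Training 2 sessions, and descriptive summaries from Training 1 sessions. If they disagreed, a reader could not tell why. At stake is the time course within each arm for objective 3, which is an explicit output: the SAP asks for estimates by arm as well as differences between arms.

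**Working it through.** **1. Programme at each visit.** The Appendix 2 table follows programme = ((visit − 5) mod 3) + 1 in all 38 rows.

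| Visit | Programme | Use in the SAP |
|---|---|---|
| V5 | 1 | baseline |
| V14 | 1 | model and descriptive |
| V28 | 3 | model only |
| V29 | 1 | descriptive only |
| V41 | 1 | descriptive only |
| V42 | 2 | model only |

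This reproduces the SAP's own statement that V5, V14, V29 and V41 are all on programme 1. Two of the three model visits do not match V5.

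**2. All visits.** V6 to V42 is 37 sessions: 12 on Training 1, 13 on Training 2 and 12 on Training 3. So (13 + 12)/37 = 25/37 = 67.6% are not on V5's programme. If only V14, V28 and V42 entered the model, 2 of 3 would not be.

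**3. Effect on within-arm change.** Let p2 and p3 be the mean offsets of Training 2 and 3 against Training 1. The change from V5 is shifted by 0 at V14, p3 at V28 and p2 at V42. With equal weight per visit, the all-visits arm mean is shifted by (13·p2 + 12·p3)/37. The documents do not give p2 or p3, so the values below are assumptions, in watts.

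| p2, p3 | V14 | V28 | V42 | All 37 sessions |
|---|---|---|---|---|
| 5, 10 | 0 | +10 | +5 | (65 + 120)/37 = +5.0 |
| 15, −5 | 0 | −5 | +15 | (195 − 60)/37 = +3.65 |
| 10, −10 | 0 | −10 | +10 | (130 − 120)/37 = +0.27 |

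The last row shows that opposite offsets nearly cancel over all visits while each single visit is still shifted.

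**4. Effect on contrasts between arms.** All trained arms ride the same programme at a given visit. With an additive offset p and true changes a and b, the contrast is (a + p) − (b + p) = a − b, so the bias is 0. With a multiplicative factor k, true contrast C and V5 arm difference D, the reported contrast is k(C + D) − D = kC + (k − 1)D. As an assumption, take V5 means of 300 and 280 (D = 20) and no true change (C = 0). The contrast at V28 or V42 is then 0.4, 1.0 or 2.0 for k = 1.02, 1.05 or 1.10. If arms are equal at V5, the contrast is only multiplied by k.

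**5. Would a programme term help?** Programme is a function of visit. For the three arms named, visit and visit-by-arm already span all 3 × 37 = 111 cells. The rank of the design is 111 without a programme term, 111 with it, and 111 with programme-by-arm added. The term is fully aliased.

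**6. Matched visits.** At V14, V29 and V41 the programme is 1, as at V5, so the offset is 0 at each.

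**The case against.** The strongest defence is that the study's question concerns arms. Protocol 2.2 asks whether switching influences the ability to perform training, and SAP 9.6.1.1.3 directs the reader to a list of arm comparisons. By step 4 those are protected from any additive programme effect. This stands, and it confines the point to within-arm changes and their time course. A reader might infer that the arm comparisons are biased. The documents do not support that: it would take a non-additive programme effect and, for a spurious contrast where none exists, an arm difference at V5 as well. Protocol 12.5 says "The exercise intensity will be the endpoint with baseline exercise intensity, age, visit, sex and arm as covariates", whereas the SAP model lists no V5 value that might absorb part of such an effect. That is a separate discrepancy, which the fix below does not address.

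Secondly, matched information already exists. SAP 9.6.1.2.3 summarises the endpoints on programme 1, and 9.1.2 attaches a 95% confidence interval to each arm mean. This stands in part: those summaries lack the model's covariate adjustment and contrasts.

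Thirdly, the effect may be small. Every session lasts 40 minutes at 60–85% intensity (Protocol 7.6.3), set by heart rate. That is possible but cannot be checked without the manual.

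Fourthly, SAP 9.1.3.1 names exercise training data as an example analysed by month. After V5, Months 1, 2 and 3 hold 3/3/3, 4/5/5 and 5/5/4 sessions of Training 1/2/3, so monthly means would be nearly comparable with each other, though each, including Month 1, would still be set against a single Training 1 session. The intensity model's text and code are written by visit, while the step-count code uses month, so the by-visit reading is likelier.

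**Conclusion.** The point holds for within-arm change from V5 at V28 and V42, and for the all-visits arm means wherever they are tabulated. The visit mismatch is certain from Appendix 2: 2 of 3 reported visits and 25 of 37 post-V5 sessions. Its numerical consequence is unknown in size and direction, and every offset and factor in the working is an assumption.

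Three stronger readings are tempting and not supported:
- That the fault is a missing programme term. Such a term is aliased with visit and would change nothing; the fault is the choice of reported visits.
- That the all-visits means are shifted by a material amount. They may be, but opposite offsets could leave almost no net shift.
- That Table 15.2.2.3.1 holds the all-visits estimates. Its title covers only V14, V28 and V42.

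This is a modest inconsistency in one objective of a descriptive study. It is worth correcting because the SAP already states the rule that its model breaks.

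**What to change.** - In SAP 9.6.1.1.3, report the model estimates and contrasts at V14, V29 and V41 in place of V14, V28 and V42.
- Change the title of Table 15.2.2.3.1 to match.
- State that V29 is taken as the end-of-month-2 point, although 9.1.3.1 ends Month 2 at V28 and so places V29 in Month 3. SAP 9.6.1.2.3 plots V29 against month but does not say which month it represents.
- Footnote the all-visits arm means, wherever they appear, as averages over mixed programmes that are not a like-for-like change from V5. If only the three reported visits are fitted, moving them to V14, V29 and V41 makes this footnote unnecessary.

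The cost is two visit labels, one table title, one sentence and one footnote. No new data or models are needed. SAP section 1 says that a changed table title needs no SAP amendment and that changes to the analyses are to be documented in the study report. The downside is that V29 falls one session after, and V41 one session before, the nominal month end.
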